### 2.2.1 Major deviations related to randomization procedure

Major deviations related to randomization procedure occur whenever:

1. A randomization is not in accordance with the protocol-defined randomization method, such as a) an ineligible patient is randomized, b) a patient is randomized based on an incorrect stratum, c) a patient is randomized twice, or d) in a dynamic randomization scheme the treatment assignment is, in fact, not random, due to a computer program error.

OR

2. A patient is dispensed an IMP kit not allocated by the protocol-defined randomization, such as a) a patient at any time in the study is dispensed a different treatment kit than as randomized (which may or may not contain the correct-as-randomized IMP), or b) a nonrandomized patient is treated with IMP reserved for randomized patients.

Major deviations related to randomization procedure will be monitored throughout the study and reviewed on an ongoing basis.

All major deviations related to randomization procedure will be documented in the CSR. The deviations will be categorized and summarized among randomized patients (number and percentages). Nonrandomized, treated patients will be described separately.

## **2.3 ANALYSIS POPULATIONS**

Patients treated without being randomized (patients who received IMP without calling the IRT or before calling the IRT, or patients who did not give their informed consent) will not be considered as randomized. They will be excluded from any population for analysis, including efficacy and safety. However, if these patients experience any safety event, they will be presented and listed separately in the appendix of the CSR.

The randomized population includes any patient who has been allocated to a randomized treatment regardless of whether the treatment kit was used.

For any patient randomized more than once, only the data associated with the first randomization will be used in any analysis population. The safety experience associated with any later randomization will be assessed separately.

### **2.3.1 Efficacy populations**

Efficacy analyses will be based on the ITT population, defined as all randomized patients, irrespective of compliance with the study protocol and procedures. Efficacy analyses will be based on the treatment group allocated by the IRT according to the randomization schedule at randomization visit (as randomized), irrespective of the treatment actually received.

### **2.3.2 Safety population**

Safety analyses will be based on the safety population, defined as all randomized patients who receive at least 1 dose of IMP (regardless of the amount of treatment administered). Patients will be analyzed for safety analyses according to the treatment actually received. For a patient randomized to a SAR425899 treatment arm, the patient will be analyzed in the treatment he/she receives starting Week 8 visit (inclusive) when no adjustment of dose level is allowed. However, for a patient randomized to a SAR425899 treatment arm and discontinues the IMP before Week 8 visit, the patient will be analyzed in the SAR425899 treatment arm the patient is randomized to. If a patient is exposed to more than one dose level of SAR425899 since Week 8 visit or later, then the patient will be analyzed in the dose level administered on Week 8 visit or study day 56 if Week 8 visit is not available. If a patient is treated with both placebo and SAR425899 any time during the study, the patient will be analyzed in the SAR425899 treatment arm. Liraglutide patients will be included in the Liraglutide treatment arm regardless of dose amount patients receive.

In addition:

- Nonrandomized but treated patients will not be part of the safety population; however, their safety data will be presented separately;

- Randomized patients for whom it is unclear whether they took the IMP will be included in the safety population as randomized;
- Patients will be excluded from the safety population only if there is documented evidence (ie, all study dates recorded as no medication taken) that patients have not taken the study medication.

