8.1.1 SAR425899 or matching placebo (solution for injection)

- Pharmaceutical form: SAR425899 solution for injection or matching placebo are supplied as cartridges containing 3 mL solutions for injection containing:
 - For SAR425899: SAR425899 at a concentration of 0.5 mg/mL in sodium dihydrogen phosphate dihydrate, di-sodium hydrogen phosphate dodecahydrate, sodium chloride, m-cresol, HCL/NaOH and water for injection,
 - For SAR425899 placebo: sodium dihydrogen phosphate dihydrate, disodium hydrogen phosphate dodecahydrate, sodium chloride, m-cresol, HCL/NaOH and water for injection.
- Route and method of administration: SC injection using the pen-type injector (Tactipen®).
- Dose of IMP per administration:
 - For SAR425899 and matching placebo, patients will be randomized to following dose regimen :
 - Low dose: 1 step weekly dose increase (if no significant tolerability issues [example, nausea and vomiting] are observed): 0.06 mg ie, 12U – 0.12 mg ie, 24U (0.12mg ie, 24U for 25 weeks).
 - Mid dose: 2 step weekly dose increase (if no significant tolerability issues [example, nausea and vomiting] are observed): 0.06 mg ie, 12U – 0.12 mg ie, 24U – 0.16 mg ie, 32U (0.16 mg ie, 32U for 24 weeks).
 - High dose: 3 step weekly dose increase (if no significant tolerability issues [example, nausea and vomiting] are observed): 0.06 mg ie, 12U – 0.12 mg ie, 24U – 0.16 mg ie, 32U – 0.20 mg ie, 40U (0.20 mg ie, 40U for 23 weeks).
- Timing: doses of SAR425899 and placebo should be injected in the morning at the same time every day except on clinic visit days.
- On clinic visit days, SAR425899 and placebo injection time should be after blood tests/ECG measurement time in the morning and be coordinated with the meal test/PK sampling time.

If the target dose is not tolerated, the study treatment can be decreased. Another attempt for dose increase may take place within 4 weeks and before Week 8 of treatment. Then, if the patient cannot reach or tolerate the target dose, he/she remains at the lower dose. If he/she cannot tolerate the lower dose, end of treatment assessments are done. Then, the patient will be discontinued from IMP but continues in the study and is followed up according to the study procedures as specified in this protocol (except for the post-treatment follow-up), up to the scheduled date of study completion. After Week 8, if the dose is no longer tolerated, final on-treatment visit assessments are done and the patient is discontinued from the IMP.

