
SAP version number	Date approved	Rationale	Description of statistical changes
1	This version	To be consistent with company standard.	The definition of treatment compliance was changed, with above-planned dosing defined as any day that the patient took a higher dose than planned, and under-planned dosing defined as any day that the patient took a lower dose than planned.
1	This version	Trend tests on HbA1c will be performed instead pairwise comparison of each dose of SAR425899 versus placebo for primary analysis. Same changes are also made for body weight analyses. The hierarchical testing procedure is also updated to reflect the changes.	Trend tests on HbA1c will be performed instead pairwise comparison of each dose of SAR425899 versus placebo for primary analysis. Same changes are also made for body weight analyses. The hierarchical testing procedure is also updated to reflect the changes. Details of the trend tests and hierarchical testing procedure are presented in Section 2.4.4 .
1	This version	Unblinded analyses results on body weight, HbA1c and FPG, and unblinded DMC results (including demographics, disposition, and safety summary) and additional related exploratory analyses will/may be provided to Sanofi internal project planning personnel to support compound development during the 2 interim analyses of the study.	Unblinded analyses results on body weight, HbA1c and FPG, and unblinded DMC results (including demographics, disposition, and safety summary) and additional related exploratory analyses will/may be provided to Sanofi internal project planning personnel to support compound development during the 2 interim analyses of the study. Details are presented in Section 3 .
1	This version	To account for the situation that a patient took a SAR425899/placebo dose level that is different from the planned 4 doses levels allow for the study, specify that if a patient is exposed to more than one dose level of SAR425899 since Week 8 visit or later, then the patient will be analyzed in the dose level administered on Week 8 visit or study Day 56 if Week 8 visit is not available.	Patients will be analyzed for safety analyses according to the treatment actually received. If a patient is exposed to more than one dose level of SAR425899 since Week 8 visit or later, then the patient will be analyzed in the dose level administered on Week 8 visit or study Day 56 if Week 8 visit is not available.

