#### *Observation period*

The observation period will be divided into 4 epochs:

- The **screening** epoch is defined as the time from the signed informed consent date up to the first administration of the IMP.
- The **treatment** epoch is defined as the time from the first administration of the IMP to the last administration of the IMP
- The **residual treatment** epoch is defined as the time from the last administration of the IMP up to 3 days (1 day for hypoglycemia, 28 days for anti-SAR425899 antibody) after the last administration of IMP.

The treatment-emergent adverse event (TEAE) period will include both **treatment** and **residual treatment** epochs.

- The **posttreatment** epoch is defined as the period of time starting the day after the end of the treatment-emergent adverse event period up to the end of the study (defined as last protocol-planned visit or the resolution/stabilization of all serious adverse events (SAE) and adverse events with prespecified monitoring as defined in protocol).

The on-study observation period is defined as the time from the start of treatment until the end of study (defined as the last scheduled visit for those who completed the study and the date collected on e-CRF page “Completion of End of Study/Follow-up” for those who did not complete the study, or the resolution/stabilization of all serious adverse events and adverse events with prespecified monitoring as defined in the protocol whichever is the latest).

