### **2.4.5.2 Analyses of adverse events**

#### ***Generalities***

The primary focus of AE reporting will be on treatment-emergent adverse events (TEAEs). Pre- and post-treatment AEs will be described separately.

If an AE date/time of onset (occurrence, worsening, or becoming serious) is incomplete, an imputation algorithm will be used to classify the AE as pre-treatment, treatment-emergent, or post-treatment. The algorithm for imputing date/time of onset will be conservative and will classify an AE as treatment-emergent unless there is definitive information to determine it is pre- or post-treatment. Details on classification of AEs with missing or partial onset dates are provided in [Section 2.5.3](#).

Adverse event incidence tables will be presented by SOC, HLGT, HLT, and PT, sorted by the internationally agreed order for SOCs and alphabetic order for HLGT, HLT and PT within a SOC, the number (n) and percentage (%) of patients experiencing an adverse event. Multiple occurrences of the same event in the same patient will be counted only once in the tables within a treatment phase. The denominator for computation of percentages is the safety population within each treatment group.

Sorting within tables ensures the same presentation for the set of all adverse events within the observation period (pretreatment, treatment-emergent, and posttreatment). For that purpose, the table of all treatment-emergent adverse events presented by primary SOC and PT (sorted by the internationally agreed SOC order and decreasing frequency of PTs within SOCs in the SAR425899 0.20 mg group) will define the presentation order for all other similar tables unless otherwise specified. In case of equal frequency regarding PTs, alphabetical order will be used.

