### ***Analysis of all treatment-emergent adverse events***

The following TEAE summaries will be generated for the safety population.

- Overview of TEAEs, summarizing number (%) of patients with any:
  - TEAE,
  - Serious TEAE,
  - TEAE leading to death,
  - TEAE leading to permanent treatment discontinuation;
- All TEAEs by primary SOC, showing number (%) of patients with at least 1 TEAE, sorted by internationally agreed order of primary SOCs;
- All TEAEs by PT, showing number (%) of patients with at least 1 TEAE, sorted by decreasing incidence of PT in the SAR425899 0.20 mg group;
- All TEAEs by primary SOC, HLGT, HLT and PT, showing number (%) of patients with at least 1 TEAE, sorted by internationally agreed SOC order. The other levels (HLGT, HLT, PT) will be presented in alphabetic order;
- All TEAEs by primary SOC and PT, showing number (%) of patients with at least 1 TEAE, sorted by internationally agreed SOC order and decreasing incidence of PTs within a SOC in the SAR425899 0.20 mg group. This sorting order will be applied to all other similar tables, unless otherwise specified;
- Common TEAEs (PTs with an incidence  $\geq 3\%$  in any treatment group) by primary SOC, HLGT, HLT, and PT, sorted by internationally agreed order of SOCs. The other levels (HLGT, HLT, PT) will be presented in alphabetic order;
- All TEAEs regardless of relationship and related to IMP by primary SOC, HLGT, HLT, and PT, showing number (%) of patients with at least 1 TEAE, sorted by internationally agreed order of SOCs. The other levels (HLGT, HLT, PT) will be presented in alphabetic order;
- All TEAEs by maximal severity, presented by primary SOC and PT, showing number (%) of patients with at least 1 TEAE by severity (ie, mild, moderate, or severe), sorted by sorting order defined above;
- Kaplan-Meier curves will be provided, when appropriate, for the time to first onset of the following PTs: nausea and vomiting;

- Summaries of common TEAEs (PTs with an incidence  $\geq 3\%$  in any treatment group) will be provided as appropriate by primary SOC, HLGT, HLT, and PT and by demographic factors including gender (Male, Female), age group ( $<50$ ,  $\geq 50$  to  $<65$ ,  $\geq 65$  to  $<75$ ,  $\geq 75$  years of age), and race (American Indian or Alaska Native, Asian/Oriental, Black, Native Hawaiian or Other Pacific Islander, White, Other). SOC will be sorted by internationally agreed order and the other levels (HLGT, HLT, PT) in alphabetic order.

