## ***Listings***

Supportive AE listings will be provided as appropriate for all AEs, SAEs and AEs leading to treatment discontinuation, TEAE leading to death, AESI, pancreatic events, major cardiovascular events, and adverse events related to local intolerability at the injection site. These listings will include at least the following information, sorted by treatment, patient identification, and onset date: treatment, patient identification, country, age, gender, race, BMI, primary SOC, PT, reported term, onset date, study day (relative day to the start date of treatment), AE duration, duration of exposure, intensity, corrective treatment, action taken with IMP, date of treatment discontinuation (if relevant), relationship to IMP/NIMP/study procedures, outcome, date of death (if any), seriousness, seriousness criteria, and AE status (“Pre” for a pre-treatment AE; “T” for a TEAE; and “Post” for a post-treatment AE).

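### By-dose safety tables group SAR425899 patients by their Week 8 dose, so an adverse event that led to a step-down is counted under the lower dose, and no as-randomized TEAE display is planned in the visible text

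*SAP*

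**What the plan says.** Safety grouping (SAP 2.3.2): for a patient randomized to SAR425899, "the patient will be analyzed in the treatment he/she receives starting Week 8 visit (inclusive) when no adjustment of dose level is allowed". Protocol 11.3.2 has the same base rule. A patient who stops IMP before the Week 8 visit stays in the randomized arm. For the comparator, "Liraglutide patients will be included in the Liraglutide treatment arm regardless of dose amount patients receive".

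Step-down (Protocol 8.1.1): the dose may be lowered if the target is not tolerated, and one more attempt to increase it may be made before Week 8. "Then, if the patient cannot reach or tolerate the target dose, he/she remains at the lower dose". After Week 8, intolerance leads to stopping IMP, not to a lower dose.

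Counting of events: in SAP 2.1.4 the treatment "epoch is defined as the time from the first administration of the IMP to the last administration of the IMP", and TEAEs include everything from that start. SAP 2.4.5.2 adds that "The denominator for computation of percentages is the safety population within each treatment group". It also plans that "Kaplan-Meier curves will be provided, when appropriate, for the time to first onset of the following PTs: nausea and vomiting".

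The visible SAP uses randomized groups for efficacy, PD and other biomarkers, PROs, demographics and disposition. It plans no TEAE table by randomized arm.

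**The concern.** The grouping variable is fixed at Week 8, after the early period in which the dose is raised. For a patient still on a reduced dose, it is set by tolerability, which is the outcome being tabulated. A patient randomized to 0.20 mg who had nausea there, went down to 0.16 mg and was still on it at Week 8 leaves the 0.20 mg column together with the event.

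The rule is also uneven:

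- A patient who stops IMP before Week 8 because of nausea stays in the randomized column. One who steps down for the same event moves.
- Liraglutide patients never move, so per-dose comparisons with liraglutide are affected too.
- Baseline tables are by randomized group (SAP 2.4.1), so columns with the same dose label can hold different patients in the baseline and AE tables.

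Safety is a main secondary objective of a dose-ranging trial. The by-dose TEAE tables and the nausea and vomiting curves are where a reader looks for a gradient.

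**Working it through.** **Reading of the rules.** Intolerance permits a step-down (Protocol 8.1.1). The dose received from Week 8 sets the column (SAP 2.3.2). Events count from the first injection (SAP 2.1.4). Numerator and denominator both use that column (SAP 2.4.5.2). It follows that a TEAE at the higher dose that led to a lasting step-down is reported under the lower dose.

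**Who is not affected.** Patients back at target by Week 8; patients who stop IMP before Week 8; pooled SAR425899 comparisons; efficacy. An event at a titration dose in a patient who never went higher is not mislabelled.

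**Size.** The plan states no figure on this point. The one design input is 60 patients per SAR425899 arm (SAP 1.3). The rest is assumed for illustration:

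- Nausea in 40/30/20% by randomized arm (0.20/0.16/0.12 mg), that is 24, 18 and 12 cases.
- A share *d* of cases has poor tolerability, and a share *k* of these stops IMP before Week 8 and is not moved. The share one level lower at Week 8 is *m* = *d*(1 − *k*).

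Rates under the Week 8 rule:

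- 0.20 mg: (24 − 24m)/(60 − 24m)
- 0.16 mg: 24m enter and 18m leave, giving (18 + 6m)/(60 + 6m)
- 0.12 mg, A (patients on 0.06 mg leave the column): (12 + 6m)/(60 + 6m)
- 0.12 mg, B (they stay in it): (12 + 18m)/(60 + 18m)

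| m | 0.20 mg | 0.16 mg | 0.12 mg, A | 0.12 mg, B | High − low, A | High − low, B |
|---|---|---|---|---|---|---|
| 0 | 40.0% | 30.0% | 20.0% | 20.0% | 20.0 | 20.0 |
| 0.1 | 21.6/57.6 = 37.5% | 18.6/60.6 = 30.7% | 12.6/60.6 = 20.8% | 13.8/61.8 = 22.3% | 16.7 | 15.2 |
| 0.2 | 19.2/55.2 = 34.8% | 19.2/61.2 = 31.4% | 13.2/61.2 = 21.6% | 15.6/63.6 = 24.5% | 13.2 | 10.3 |

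With *d* = 0.2 and half of these stopping before Week 8, *m* = 0.1 and the middle row applies.

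At *m* = 0.2, 4.8 patients move from 0.20 to 0.16 mg and 3.6 from 0.16 to 0.12 mg. That is 8.4 of the 54 nauseated patients; 2.4 more go to 0.06 mg.

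**Dose order.** The 0.20 and 0.16 mg rates are equal when 36(60 + 6m) = 42(60 − 24m), so 1224m = 360 and m = 0.294. A change of order would need about 29% of all nauseated patients, mild cases included, to be on a reduced dose at Week 8.

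**A harsher case.** Suppose only the 0.20 mg arm steps down, 6 of 60 do so, all six had the event, and everyone else has a 30% rate. As randomized, 0.20 mg has (6 + 0.3 × 54)/60 = 37.0% against 30.0% for 0.16 mg, a difference of +7.0 points. By Week 8 dose it is 16.2/54 = 30.0% against 24/66 = 36.4%, or −6.4 points. The reversal is built into those assumptions, and the conclusion does not rest on it.

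**The case against.** The strongest case on the other side is that analysis by treatment received is prespecified in both documents, that safety is descriptive (SAP 2.4.5), and that an as-randomized table has its own distortion: it credits titration-period events, and later exposure at a reduced dose, to a dose the patient may hardly have taken or never reached. That stands, and it is why the Week 8-dose display should be kept. It also means that *m* above mixes patients who stepped down with patients who never escalated. For the latter the Week 8 label is fair, so 8.4 of 54 overstates the truly relabelled events by an unknown amount.

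Several outputs offset the problem in part:

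- Patients not treated as randomized are listed, and discontinuations with reasons are given on randomized denominators (SAP 2.2). Curves of IMP discontinuation due to AE are planned there too, but a step-down is not a discontinuation.
- AE listings carry "study day (relative day to the start date of treatment), AE duration, duration of exposure, intensity, corrective treatment, action taken with IMP". The stated minimum items include neither randomized arm nor dose at onset.
- PK/safety work on nausea and vomiting is possible (SAP 3), but plasma is sampled only at Weeks 14 and 26 (Protocol 9.3.1.1).
- SAP 2.4.5 leaves room for further subgroups without committing to this one.

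Together these allow patient-by-patient tracing, not a group comparison. SAP Appendix B and the separate DMC SAP are not available here and could hold more, so the statement about a missing display is limited to the visible text.

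On 0.06 mg, SAP Table 2 has in view the case that "a patient took a SAR425899/placebo dose level that is different from the planned 4 doses levels allow for the study", which counts 0.06 mg among the planned levels. The three SAR425899 groups named in the efficacy model do not define safety columns, so a literal reading would give 0.06 mg its own group (variant A). SAP 2.3.2 does not say so; this is a missing detail, not a main point.

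**Conclusion.** The concern holds. For SAR425899 patients still on a reduced dose at Week 8, the by-dose TEAE tables and the nausea and vomiting curves are grouped by a status that depends on the outcome. The effect is to flatten a dose-tolerability gradient, and a reader could detect this only by tracing individuals through listings.

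The reading of the rule is firm; the size is not known. Under the assumed 40/30/20% rates, a 20-point gradient reads as 15.2 to 16.7 points at a 10% share and 10.3 to 13.2 points at a 20% share, taking the as-randomized figures as reference. No change in dose order is claimed. The point should be fixed, but it does not touch efficacy or the validity of the trial.

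**What to change.** In SAP 2.4.5.2 add:

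> The TEAE overview, TEAEs by primary SOC and PT, common TEAEs, TEAEs by maximal severity, and the Kaplan-Meier curves for nausea and vomiting will also be presented by randomized SAR425899 arm.

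Keep the Week 8-dose display beside it, because a patient on a reduced dose at Week 8 can spend about 26 − 8 = 18 of the 26 weeks on that dose. Note under the new tables that they attribute titration-period and reduced-dose events to the assigned dose.

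In SAP 2.3.2 state which column holds patients on 0.06 mg at Week 8.

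A table by dose at onset is optional. If given, it should warn that dose is confounded with time on treatment, since every SAR425899 arm starts at 0.06 mg and passes through the lower doses first.

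The cost is SAP wording and a few extra tables and curves from data already held. No dosing rule changes.
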